Title: The Effect of Guanfacine on Delirium in Critically Ill Patients

Primary Investigator: [name]

University of Alabama at Birmingham Department of Anesthesiology and Perioperative Medicine, Division of Critical Care Medicine Contact: [contact]

[contact]

[name] is a full-time faculty member of the University of Alabama at Birmingham's Department of Anesthesiology and Perioperative Medicine and holds the academic standing of Associate [name] has basic science research experience and maintains a strong interest in medical education and clinical research.

NCT04578886

Date Aug 18, 2019

Location of Study: Research will be conducted at the University of Alabama at Birmingham Hospital and University of Alabama at Birmingham Highlands Hospital. Patients will be recruited in the UAB Surgical Intensive Care Units.

Abstract

Delirium has been identified as a significant problem in the intensive care unit that has been shown to lead to increased hospital and ICU length of stay, increased hospital cost, increased ventilator days, and long-term cognitive disability. The etiology of delirium is multifactorial, however, the elderly critically ill remain at highest risk. Therapy is largely targeted at nonpharmacologic prevention as promising treatments have not been standardized.

One such pharmaceutical treatment is the medication dexmedetomidine. Originally designed as an antihypertensive, dexmedetomidine is a central acting alpha agonist used as a sedation adjunct and has shown to reduce the duration of delirium in the intensive care setting. Guanfacine, a medication with the same mechanism and within the same class as dexmedetomidine, has a more specific sight of action in the frontal lobe and therefore more behavior modification properties. For this reason, guanfacine has been shown to be an effective adjunct therapy in Attention Deficit Hyperactive Disorder and has a secondary FDA approval for its use in that behavior disorder.

One of the hallmark symptoms of delirium is inattention and hyperactive behavior. Given the similarities between delirium and hyperactive disorders, guanfacine has been identified as a potential medication that may be of therapeutic benefit in the treatment of delirium. It is the purpose of this study to investigate the effects of guanfacine on delirium in critically ill patients admitted to the ICU.

Null Hypothesis

The administration of guanfacine in ICU patients with delirium will not reduce the duration of delirium.

Hypothesis

The administration of guanfacine in ICU patients with delirium will reduce the duration of delirium.

Specific Aim

To quantify the duration of delirium in ICU patients treated with guanfacine or placebo.

Trial design

The study will be a prospective, single center, randomized, placebo-controlled, double- blind, intervention trial of guanfacine 2 mg versus placebo in critically ill patients admitted to the ICU with an expected LOS of at least 72 hours. (two arms, 1:1 enrollment, parallel design).

Methods

Inclusion criteria

- Patients admitted to the UAB hospital Surgical Intensive Care Unit (SICU)
- 18 years of age or older

- Expected total ICU length of stay of 72 hours or more per treating physician
- Diagnosed with delirium based on CAM-ICU assessment (see attached CAM-ICU assessment form)

Exclusion Criteria

- Patients younger than 18 years old
- Expected discharge from ICU within 72 hours of admission
- Expected or inevitable death with 48 hours of enrollment
- Pregnancy or breast feeding
- Non-English speaking
- Patients unable to be assessed by CAM-ICU due to neurologic illness
- Altered consciousness unable to participate in CAM-ICU assessment
- Patients with previous diagnosis of chronic, acute, subacute neurologic disease, or neurodegenerative disease
- Mental illness and/or psychosis
- Acute alcohol withdrawal
- No enteral route available for administration
- Treating physician refusal of enrollment based on severe hypotension (defined as requiring a vasopressor for longer than 24 hours) or bradycardia (Hr<50 bpm) at the time of screening
- Hepatic encephalopathy
- Blind or Hearing impaired
- Taking Guanfacine, for any reason
- On CYP3A inhibitor such as azole antifungals or clarithromycin
- On CYP3A inducers such as phenytoin or rifampin
- Severe xerostomia
- Enrolled in another interventional research trial

Intervention

-After patient or family member signs the informed consent

-Patients are enrolled within 48 hours of being diagnosed with delirium

-Randomization to placebo or study drug group on the day of enrollment

-Placebo group will receive pharmaceutical placebo.

-Guanfacine group will receive guanfacine 2 mg enterally via oral route or

nasogastric tube at 21:00 for 14 consecutive nights or until ICU discharge.

-CAM-ICU assessment will be conducted twice daily at am and pm. All data was deidentified and entered in secured RedCap database.

Outcomes

Primary

Duration of delirium

The primary outcome will be the number of days alive without delirium during the 14-day treatment period after randomization. Delirium assessments are measured by the Confusion Assessment Method- Intensive Care Unit (CAM-ICU). CAM-ICU measures a patient's fluctuations in mental status, inattention, disorganized thinking, and consciousness.

All assessors using the CAM-ICU will receive training in the assessment tool along with monitoring to ensure the reliable implementation. The CAM-ICU will be used twice daily with all patients while admitted until ICU discharge. Patients will be diagnosed as delirious when they have at least one positive CAM-ICU on the day of assessment up to ICU discharge or day 14 after enrollment if remaining in ICU. Patients will be diagnosed as delirium free when they have four (4) negative consecutive CAM-ICU assessments. Assessors will be blinded to treatment group.

Secondary

1. Type of delirium or Coma

Based on patient RASS score, the participants will be categorized as having either hyperactive delirium (RASS >+1) or hypoactive delirium (RASS -3 to 0), Mixed (both hyperactive and hypoactive for the observation period), or Coma (RASS </= -4.

- 2. Duration of delirium Upon diagnosis of delirium, duration will be recorded as number of days of which the enrolled patient has a positive CAM-ICU until ICU discharge or day 14 after enrollment.
- Delirium Severity
 Assessors will administer the CAM-ICU-7 Delirium Severity assessment.
 Indirect markers of delirium severity will also be recorded daily until ICU discharge or day 14 after enrollment. These markers are: 1) need for anti-psychotics or sedation (total daily doses will be calculated); 2) need for physical restraints; 3) patient removal of intravenous lines, drains or catheters.
- 4. ICU and hospital LOS

Length of stay will be recorded using existing hospital data programs.

5. Morbidity and mortality

Markers of morbidity and mortality will be recorded on a daily basis until ICU discharge or day 14 after enrollment. These include: 1) duration of mechanical ventilation measured as ventilator free days; 2) daily need for vasopressor use; 3) daily need for renal replacement therapy; 4) reintubation, delayed extubation or need for tracheostomy; 5) SOFA scores; In addition we will record 6) mortality at 30 and 90 days; and 7) destination after ICU and hospital discharge.

Analysis

Statistical Analysis. Demographics, such as gender, race, and age, as well as clinical characteristics (such as type of surgery, comorbidities) will be summarized using descriptive statistics. Continuous variables will be summarized using sample mean and sample variance whereas categorical variables will be summarized as proportions. The test of efficacy will follow the rejection region approach detailed in the Sample Size section using a Type I error rate of 0.05. 95% confidence intervals will be used to describe the incidence of delirium within the study population. Logistic regression models will examine whether age, gender, or comorbities associated with incidence of delirium when Guanfacine is administered.

Projected Sample Size. The primary outcome for statistical evaluation is delirium free days, defined as the number of days out of a 14-day period following enrollment. Power analyses are based on this outcome.

Based upon the historical evidence observed in the UAB Surgical ICU, delirium is experienced by approximately 24% of patients during their ICU stay.

All sample size and power estimates below assume a two-group, parallel design with 1:1 allocation ratio. In Table 1, we treat the primary outcome as number of delirium-free days during each patient's LOS.

We consider a range of detectable differences and desired levels of power in Table 1 below. The analysis consists of a two-sample t-test assuming equal variances and evaluation at a 0.05 level of significance. A mean difference of 10% is considered clinically meaningful, with larger differences indicating greater benefit. However, we do not have preliminary data providing reference values for the average and standard deviation of delirium free days in the control population. Thus, we express our detectable differences in terms of standard deviations between the two groups.

A sample size of 50 per group (100 total) will provide 85% power to detect an average proportion of delirium-free days in the treatment group that is at least 0.61 standard deviations different from the average proportion of delirium-free days in the control group.

Total(n)	Power	
	80%	85%
100	0.57	0.61
90	0.60	0.64
80	0.63	0.68

Table 1. Detectable Δ (standard deviation) with new sample size.

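### Bradycardia, blood pressure, held doses and adverse events are not listed outcomes, hypotension is captured only through vasopressor need (and possibly SOFA), and no by-arm safety summary is planned

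*Combined protocol and SAP*

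**What the plan says.** - **Exclusion Criteria.** One criterion rests on the treating physician declining enrolment because of "severe hypotension (defined as requiring a vasopressor for longer than 24 hours) or bradycardia (Hr<50 bpm"). It is a ground for physician refusal, and it applies only at screening: "bradycardia (Hr<50 bpm) at the time of screening".
- **Abstract.** The drug is introduced as "a medication with the same mechanism and within the same class as dexmedetomidine", and dexmedetomidine is said to have begun as a blood-pressure-lowering agent.
- **Intervention.** Study drug is given nightly "for 14 consecutive nights or until ICU discharge".
- **Outcomes, Secondary, item 5.** "Markers of morbidity and mortality will be recorded on a daily basis until ICU discharge or day 14 after enrollment". The items are ventilator-free days, vasopressor need ("2) daily need for vasopressor use"), renal replacement therapy, reintubation or delayed extubation or tracheostomy, SOFA scores, 30- and 90-day mortality, and discharge destination. Item 1 adds a coma category based on RASS.
- **Analysis.** The text covers descriptive statistics for demographics and clinical characteristics, a test of efficacy, confidence intervals for delirium incidence, and logistic models for delirium. It has no safety analysis and no table of harms by arm.

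**The concern.** The plan names two haemodynamic conditions as reasons to keep a patient out, and gives a numeric heart-rate threshold for one of them. It then gives the drug for up to 14 nights to critically ill patients and lists no outcome that would show whether bradycardia arose on treatment. Hypotension handled without a vasopressor, for example by withholding a study dose, would not appear among the outcomes either, and neither would the withheld dose.

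Two things are at stake. If guanfacine increases delirium-free days, the report would have no planned comparison of bradycardia to set beside that benefit. If the result is null, the absence of dose records would make it hard to tell an ineffective drug from an under-delivered one.

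**Working it through.** **1. Stated risks against listed outcomes**

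| Item | Before randomisation | Listed outcome after randomisation | By-arm analysis planned |
|---|---|---|---|
| Severe hypotension (defined by vasopressor use beyond 24 h) | Ground for refusal | Daily vasopressor need; possibly SOFA (components not listed) | None stated |
| Hypotension without a vasopressor | Not mentioned | None, unless through SOFA | None stated |
| Bradycardia (HR below 50) | Ground for refusal | None | None stated |
| Study doses held or stopped | – | None | None stated |
| Adverse or serious adverse events | – | None | None stated |
| Coma, mortality | Expected death is an exclusion | RASS-based coma; 30- and 90-day deaths | None stated |

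One of the two named conditions is therefore recorded in the plan's own terms. Bradycardia has neither a direct measure nor a proxy.

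**2. The plan's own design figure**

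Inputs from Projected Sample Size: 50 per group, difference 0.61 SD, two-sample t-test with equal variances, alpha 0.05 (sidedness is not stated; two-sided is used here because it reproduces the table). The noncentral t distribution gives power 85.5%, against the stated 85%. The difference detectable with 85% power is 0.605 SD, against the stated 0.61. The figure reproduces. It concerns delirium-free days only and has no bearing on harms.

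**3. What 50 per arm could say about harms if they were recorded**

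The documents give no event rates, so every rate below is an assumption.

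*No events seen in an arm.* The exact two-sided 95% upper limit solves (1 − p)^50 = 0.025:

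p = 1 − 0.025^(1/50) = 0.071, or 7.1%.

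The one-sided 95% limit is 1 − 0.05^(1/50) = 5.8%.

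*Chance of at least one event in an arm*, 1 − (1 − p)^50:

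| Assumed true rate | Chance |
|---|---|
| 2% | 64% |
| 5% | 92% |
| 10% | 99.5% |

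*Power of Fisher's exact test*, 50 v 50, two-sided 0.05, summing the product of the two binomial probabilities over all tables with p ≤ 0.05:

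| Assumed control v guanfacine | Power |
|---|---|
| 10% v 20% | 19% |
| 5% v 15% | 24% |
| 10% v 30% | 64% |
| 10% v 35% | 82% |

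The table would thus bound rates and show large imbalances. It would not reliably detect a ten-point difference.

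**The case against.** A reader might infer that the trial cannot report its drug's foreseeable harms by arm. The documents do not support that. The plan defines severe hypotension by vasopressor use, and it records vasopressor need daily in both arms. SOFA, coma, renal replacement, reintubation and mortality are recorded too, and all can be tabulated by arm in a randomised trial.

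A reader might also infer that a bradycardia imbalance would go unseen. These are ICU patients, and their heart rate is presumably charted. Item 5 introduces its markers with wording that need not be exhaustive, and adverse-event procedures may sit in ethics or monitoring files not supplied here. Absence from the outcomes list shows that no by-arm report is specified; it does not show that nothing is observed.

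The link to the drug is also inferred. The protocol does not call hypotension or bradycardia guanfacine effects, and its remark about an antihypertensive origin describes dexmedetomidine. Finally, a single scenario such as 10% v 30% flatters what 100 patients can show.

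All of these objections stand, and they narrow the point. They leave untouched that bradycardia, blood pressure, held doses and adverse events are not listed outcomes and that no safety summary is planned. Reports held elsewhere would not by themselves supply a prespecified comparison by arm, which belongs in this document.

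**Conclusion.** The narrower point holds. The plan treats bradycardia and hypotension as enrolment concerns, then specifies no bradycardia, blood-pressure, held-dose or adverse-event outcome and no by-arm safety summary. The gap is complete among the listed outcomes for bradycardia and partial for hypotension, where daily vasopressor need covers the severe form.

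The conclusion assumes that the supplied document is the full plan for outcomes and analysis, and that the two conditions are foreseeable effects given the stated drug class. Its size cannot be given as an event rate because the documents contain none. Over the assumed rates, power to detect an imbalance runs from 19% to 82%, so the gain from closing the gap is descriptive. The primary analysis is unaffected. This is an improvement that should be made because it is cheap and changes what the trial can report; it does not invalidate the design.

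**What to change.** Add to the daily secondary outcomes, taken from the ICU chart until ICU discharge or day 14:

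- any heart rate below 50 bpm, which is the plan's own threshold;
- lowest blood pressure;
- study doses held or stopped, with the reason;
- serious adverse events.

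Add one sentence to the Analysis section: these items, together with the vasopressor need, coma and mortality already recorded, will be reported by arm as numbers of patients and risk differences with exact 95% confidence intervals, with lowest blood pressure as a summary by arm. State that the table is descriptive. A separate field for new vasopressor use is largely unnecessary, since daily need is already collected. These are recording and reporting items only; they set no rule for dosing or stopping.

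Cost: a few REDCap fields and one table, on the assumption that heart rate, blood pressure and doses given are charted routinely. Serious adverse events and reasons for held doses need some additional work to record and follow up, so the change is not free of effort. The sample size stays at 100 and the primary test is unchanged.

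### No criterion requires delirium near randomisation, so patients whose index episode may already be over can be enrolled up to 48 hours after diagnosis, which would dilute the treatment contrast

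*Combined protocol and SAP*

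**What the plan says.** Under Methods, the delirium entry criterion is "Diagnosed with delirium based on CAM-ICU assessment", with no time point attached. The Intervention list adds "Patients are enrolled within 48 hours of being diagnosed with delirium" and "Randomization to placebo or study drug group on the day of enrollment". It also sets the assessment schedule: "CAM-ICU assessment will be conducted twice daily at am and pm". None of the four inclusion or nineteen exclusion criteria asks for a positive result at or shortly before randomisation, and none removes a patient who has since turned negative.

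The Hypothesis reads: "The administration of guanfacine in ICU patients with delirium will reduce the duration of delirium".

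Outcomes, Primary counts days alive without delirium over the 14 days after randomisation. It gives two rules. For a delirious day: "Patients will be diagnosed as delirious when they have at least one positive CAM-ICU on the day of assessment". For recovery: "Patients will be diagnosed as delirium free when they have four (4) negative consecutive CAM-ICU assessments".

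The Analysis section plans a two-sample t-test with equal variances. It mentions no baseline delirium status, and the projected sample size makes no allowance for patients who have improved before randomisation.

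**The concern.** The question is whether guanfacine shortens delirium that is present. The entry rules ask only that delirium was diagnosed at some point in the preceding 48 hours. The protocol itself describes mental status in delirium as fluctuating, so a brief episode can be followed by negative assessments before the patient is randomised.

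For a patient whose index episode is over by then, treatment cannot shorten that episode. Benefit can appear only as fewer later positive days. The comparison then blends treating current delirium with preventing its return, and the average difference between arms shrinks if the drug does less for such patients. At stake are power and the match between the enrolled sample and the stated hypothesis.

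**Working it through.** **1. Timing, from the protocol's own rules.** At two assessments a day, with the diagnostic positive at hour 0, the next four fall at these hours:

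- 12/12 h spacing: 12, 24, 36, 48
- 10/14 h spacing: 10, 24, 34, 48 or 14, 24, 38, 48
- 8/16 h spacing: 8, 24, 32, 48 or 16, 24, 40, 48

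The fourth negative always falls at hour 48. The four-negative rule can therefore be met only at the limit of the window, or slightly past it, because randomisation is tied to the enrolment day and not to an hour. One to three negatives are possible well inside the window. For example, with 12/12 h spacing, a patient positive one evening and negative the next morning and evening (hours 12 and 24) has a full calendar day with no positive result. That day is not delirious under the day-level rule, yet the patient stays eligible for up to another 24 hours.

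**2. Reproducing the plan's figure.** Inputs from Projected Sample Size: 50 per group, difference d = 0.61 SD, t-test, significance level 0.05. Sidedness is not stated; two-sided reproduces Table 1. The noncentral t gives 85.5% power, against the stated 85%. All six cells of Table 1 reproduce within 0.005 SD.

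**3. Dilution.** Two assumptions are needed that the documents do not supply: 0.61 SD is the effect in patients still delirious at randomisation, and a share r of those enrolled has nothing to gain. With SD held at 1, the average effect is d = 0.61 × (1 − r). If such patients keep half the effect through fewer relapses, d = 0.61 × (1 − r/2).

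| r | d, no effect kept | Power | n per arm for 85% | d, half kept | Power |
|---|---|---|---|---|---|
| 0% | 0.610 | 85.5% | 50 | 0.610 | 85.5% |
| 10% | 0.549 | 77.6% | 61 | 0.580 | 81.8% |
| 20% | 0.488 | 67.6% | 77 | 0.549 | 77.6% |
| 30% | 0.427 | 56.1% | 100 | 0.519 | 72.8% |

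**4. Sensitivity to the SD.** Patients who have improved may also have a higher mean outcome, which widens the pooled SD. Let their mean lie 1 SD above that of the control patients still delirious, with no effect kept. The average variance is then ½[(1 + r(1 − r)) + (1 + r(1 − r)(1 − 0.61)²)]. At r = 20% this is ½(1.16 + 1.024) = 1.092, so d = 0.488/√1.092 = 0.467. Power is 75.5%, 63.8% and 51.5% at r = 10%, 20% and 30%.

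**5. Excluding against enrolling, with no extra screening.** Suppose r = 20% and excluded patients are not replaced. Then 50 × 0.8 = 40 per arm remain at d = 0.61, and power is 76.9%. Enrolling them gives 67.6% if they gain nothing and 77.6% if they keep half the effect. Exclusion is clearly better in the first case and about equal in the second, before any replacement recruitment.

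**The case against.** The strongest reply starts from the recovery rule. A patient with one to three negatives has not recovered by the protocol's definition, and four negatives fit only at the edge of the window. That stands. A reader might infer that the trial will enroll patients already recovered by its own rule, but the documents support only that some enrolled patients may have finished their index episode.

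Second, a reader might infer that such patients cannot show benefit. The documents do not support that either. Later positive days count in the primary outcome, so preventing a relapse would register. The half-effect column allows for this.

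Third, 0.61 SD is given as a detectable difference between the randomised groups, not as the expected effect in still-delirious patients. Power for a true 0.61 SD difference in whoever is enrolled remains 85%. This also stands: the power losses are conditional on the stated assumptions and are not an error in the plan's calculation.

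Fourth, randomisation spreads these patients over both arms, so there is no bias between arms, and a window that leaves time for consent is a defensible choice. Agreed. None of this supplies the missing criterion, however, or brings the entry rules into line with a hypothesis about patients with delirium.

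**Conclusion.** The gap holds: entry requires a recent diagnosis, not delirium near randomisation. The consequence is possible dilution, and a sample that only partly matches the treatment question. It is not bias.

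Its size cannot be fixed from the documents, which give neither an early recovery rate nor a mean and SD for controls. On the assumptions stated in the working, the loss from the planned 85% runs from about 3 percentage points (10% affected, half the effect kept) to about 29 (30% affected, none kept, SD held at 1). Power was below 85% in every scenario with any affected patients, but how many there would be is unknown. The absence of the criterion is certain; the power figures are illustrations. This is worth correcting because the correction is cheap.

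**What to change.** Keep the 48-hour outer window and add one inclusion criterion: *at least one positive CAM-ICU among the two most recent scheduled assessments (previous 24 hours) before randomisation*. The look-back should cover two assessments and not only the calendar day of randomisation. A same-day rule would turn away a patient randomised after a negative morning result who was positive the evening before, and that is fluctuating delirium of the kind the trial means to treat.

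Also record the last CAM-ICU result before randomisation and include it as a baseline covariate in the primary analysis. The planned t-test then becomes a linear model with treatment and this one binary term, specified before unblinding.

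The cost is one eligibility line, one data field and one model term, all using an assessment already part of the plan. The downside is slightly slower accrual, because patients with very brief delirium would not be enrolled.

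### Secondary outcome 1 places RASS +1 in no delirium type, so the subtype bands are not exhaustive and some participants are left untyped or kept out of Mixed

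*Combined protocol and SAP*

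**What the plan says.** The rule is in the combined protocol and SAP, under Outcomes, Secondary, item 1 (Type of delirium or Coma). It classifies people, and RASS is the only basis: "Based on patient RASS score, the participants will be categorized as having either" one of the listed types. The types are:

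- "hyperactive delirium (RASS >+1) or hypoactive delirium (RASS -3 to 0"), where the hyperactive cut-off is a strict inequality;
- "Mixed (both hyperactive and hypoactive for the observation period");
- Coma, at RASS -4 or lower, where the equality is written out with the symbol `</=`.

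There is no residual or unclassified category. No other section defines the subtypes, assigns a score of +1, or says how an unassigned score is handled. The Statistical Analysis paragraph says only that categorical variables will be summarised as proportions. It names no test, model or subgroup analysis that uses delirium type.

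**The concern.** A set of types reported as proportions should give every participant with delirium exactly one label. Here the hyperactive band starts above +1 and the hypoactive band stops at 0, so one score between them belongs to neither. The omission has two consequences. A participant can end up with no type. And because Mixed is built from the other two bands, the gap also decides who can be called Mixed.

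At stake is whether the subtype table can be interpreted. An analyst who programs the printed rule and one who silently treats +1 as hyperactive would report different counts from the same data, and the document does not say which is intended.

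**Working it through.** The plan gives no figure to reproduce here, so the check is to apply the rule to each possible score and then to example participants.

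**Inputs.** The three bands and the Mixed definition come from secondary outcome 1. Two assumptions are needed:

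- RASS takes whole numbers from -5 to +4. The document does not print the scale, but the gap needs only that +1 is a possible score, which the plan's own cut-off implies.
- The scores that count are those recorded when the participant is CAM-ICU positive. The document does not state this.

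**Step 1: each score against the bands.**

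| RASS | Category as written |
|---|---|
| -5, -4 | Coma |
| -3, -2, -1, 0 | Hypoactive |
| +1 | None |
| +2, +3, +4 | Hyperactive |

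Classified: 2 + 4 + 3 = 9 of 10 scores. The only gap is +1.

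**Step 2: example participants.** The label is taken over the whole observation period. The second column treats a +1 score as adding no category, which is the literal result. The last two columns show the two ways of closing the gap.

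| Scores in the period | As written | If +1 is hyperactive | If +1 is hypoactive |
|---|---|---|---|
| +1 only | No type | Hyperactive | Hypoactive |
| +1, -1 | Hypoactive | Mixed | Hypoactive |
| +1, 0 | Hypoactive | Mixed | Hypoactive |
| +1, -2, 0 | Hypoactive | Mixed | Hypoactive |
| +1, +2 | Hyperactive | Hyperactive | Mixed |
| +2, -1 | Mixed | Mixed | Mixed |
| +1, -4 | Coma | Hyperactive and Coma | Hypoactive and Coma |

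**Step 3: what follows.** Either assignment puts all 10 scores in exactly one band. The printed rule matches neither assignment throughout. Compared with +1 as hyperactive, it can only leave hyperactive participants untyped and move Mixed participants into hypoactive. The last row shows a separate matter: the rule gives no precedence when a participant has both coma and delirium scores. Closing the gap at +1 does not settle that.

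**Step 4: reach.** The primary outcome and secondary outcome 2 (duration) depend on CAM-ICU results, not on subtype. The power calculation concerns delirium-free days. A positive assessment at +1 still counts in all of these, and CAM-ICU-7 severity is still administered.

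**The case against.** The strongest reply is that this is a slip of notation, that everyone would read the cut-off as +1 or higher, and that if the trial applied it that way no count is wrong. A lost underline in the PDF conversion is also conceivable. Part of this stands: the intended cut-off may well include +1. But the same sentence writes the equality explicitly for Coma, which makes a lost symbol unlikely. Nothing elsewhere confirms the intention, and the printed rule is what an analyst would program.

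It can also be said that the document prints no RASS descriptors and cites no subtype standard, so it does not show that +1 belongs with hyperactive. That is correct. What the text supports is that +1 is unassigned and must be assigned.

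A reader might infer more than the document supports in four ways:

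- **That a sizeable share of participants goes unclassified.** The document gives no frequency for +1. A share of assessments would not convert to participants anyway, because the label covers the whole period and CAM-ICU is done twice a day. As an illustration, assume 10% to 20% of positive assessments are at +1 and that assessments are independent. With two positive assessments, both are at +1 in 0.10² = 1% to 0.20² = 4% of participants. With four, the range is 0.10⁴ = 0.01% to 0.20⁴ = 0.16%. Correlation within participants would raise these figures.
- **That the gap biases the comparison of arms, because guanfacine moves patients from +2 to +1.** A delirious +2 already recorded keeps the participant hyperactive or Mixed after a later fall to +1. The document attributes a sedation role to dexmedetomidine, and describes guanfacine in terms of behaviour. Differential loss by arm is speculation.
- **That every participant moving between +1 and a negative score becomes hypoactive.** This holds for negative scores of -1 to -3, and also for 0. Scores of -4 and -5 are Coma.
- **That delirium at +1 is lost to the trial.** Only its contribution to the subtype label is missing.

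**Conclusion.** The concern holds. As written, the subtype rule is not exhaustive. RASS +1 has no category, a participant with only +1 delirious scores has no type, and one with +1 and scores from -3 to 0 is labelled hypoactive and cannot be Mixed. The reported proportions therefore need not cover all participants, and can differ from those that exhaustive bands would give.

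The number of participants affected cannot be derived from the document. The consequence is limited to a descriptive summary of one secondary outcome. The conclusion rests on +1 being a possible score, on the cut-off being printed as intended, and, for the hypoactive label, on an unassigned score adding no category.

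**What to change.** Before unblinding, amend secondary outcome 1 so that RASS +1 belongs to a stated category, and apply the Mixed definition to the corrected bands. The natural reading is hyperactive at +1 or higher, hypoactive from -3 to 0 and Coma at -4 or lower. The sponsor should confirm that this was meant. The same edit should say which RASS scores count towards the label, and which label applies when a participant has both coma and delirium scores.

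If unblinding has already taken place, report the subtype counts both as printed and with +1 assigned, so that the choice is visible.

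The cost is a short change of wording. RASS already has to be recorded for this outcome, so no new data are needed, and the sample size and primary analysis do not change.
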